#### **Qualitative Breast Examination**

The percentage of subjects with any abnormal change in the qualitative breast examination will be summarized. The incidence of abnormal changes in these evaluations will be compared between treatment using Fisher's exact test.

#### **Blood Pressure, Pulse and DRE**

The percentage of subjects exceeding the threshold criteria for blood pressure and pulse at any post-baseline assessment will be summarized by treatment group. The percentage of subjects with any abnormal change in the DRE evaluations will be summarized. The incidence of abnormal changes in these evaluations will be compared across treatment groups using Fisher's exact test.

## Suicidality

To protect subjects in the study, scores from C-SSRS tests will be reviewed in real time by the investigator and appropriate advice given to participants.

The C-SSRS scale has 10 outcomes, with binary (yes/no) responses. At the end of study, results will be assessed as follows:

- Suicidal ideation will be defined as a positive response at any time during treatment to any one of the five suicidal ideation questions (Categories 1-5) on the C-SSRS.
- Suicidal behavior will be defined as a positive response at any time during treatment to any one of the five suicidal behaviour questions (Categories 6-10) on the C-SSRS.
- Suicidal ideation or behavior will be defined as a positive response at any time during treatment to any one of the ten suicidal ideation and behaviour questions (Categories 1-10) on the C-SSRS.

The numbers of subjects with a positive response for suicidal ideation or suicidal behaviour will be reported at baseline and during study treatment at Visits 4, 6 and 10 (6, 12 and 24 months post randomization respectively). Scores on treatment will be compared with baseline scores and, for Visits 6 and 10, with scores at last visit to determine the incidence of treatment-emergent suicidality. An increase in C-SSRS total score to 4 or 5 will be considered as serious treatment-emergent suicidality. Due to the low numbers of subjects expected to exhibit suicidal behaviours, formal statistical testing will not be performed.

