#### 7.4.2. Definition of a SAE

A serious adverse event is any untoward medical occurrence that, at any dose:

Results in death

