## 7.4.6. Suicidality Monitoring

Assessment of suicidality will be performed using the C-SSRS which will be administered at baseline, during the course of study, and at the end of the study. Training to investigators and sites on suicidality assessment will be integral to the study implementation. Any AEs which, in the investigator's opinion, are possibly suicidality-related, will be recorded in the Possible Suicidality Related Adverse Event form (PSRAE); a supplemental CRF form designed to collect detailed information on the circumstances of reported AEs related to suicidality.

The 'baseline/screening' version of C-SSRS will be used at the pre-screening visit (V1a). The 'since last visit' version of C-SSRS will be used at Visits 4, 6 and 10 (6, 12 and 24 months post randomization respectively).

A trained rater will administer the C-SSRS questionnaires according to the schedule detailed in Table 1. The C-SSRS questionnaire will be completed during the clinical visit separately from the medical history and the standard adverse event questions.

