## 9.3.4. Analysis Data Sets

Endpoints measured at specific visits and analysed in terms of visit numbers include: IPSS, Qmax, prostate volume, PSA, post void residual volume, suicidality and health outcomes. Analysis of the data collected in terms of visit numbers will be performed using two different approaches to account for missing data.

- 1. LOCF (Last Observation Carried Forward) analysis: This involves bringing (carrying) forward the last non-missing post-baseline assessment for subjects with missing visit data and/or for subjects who discontinued from the study.
- 2. At Visit analysis: Missing values at post-baseline assessments are not replaced and are regarded as missing.

The LOCF approach will be considered primary. If the LOCF and At Visit results are not consistent with regard to the statistical analyses and conclusions, then further data analyses will be undertaken.

Endpoints measured in terms of event calendar days and analyzed in terms of survival methodology include AUR and BPH-related surgical intervention. These analyses will use the observed-cases approach in which actual date of event is used; missing values post-baseline are not replaced and are regarded as missing.

Analysis datasets will be created with a structure to reflect the above noted approaches for each endpoint.

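### The C-SSRS rule for serious treatment-emergent suicidality rests on an undefined total score, so a suicide attempt need not receive that label; suicidality is also listed under LOCF

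*Protocol*

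**What the plan says.** The Suicidality text in Protocol section 9.3.7.2.1 describes the instrument: "The C-SSRS scale has 10 outcomes, with binary (yes/no) responses". Suicidal ideation is a positive on-treatment response to "any one of the five suicidal ideation questions (Categories 1-5) on the C-SSRS". Suicidal behaviour is a positive on-treatment response to "any one of the five suicidal behaviour questions (Categories 6-10) on the C-SSRS". A third outcome combines the two. On reporting, it says: "The numbers of subjects with a positive response for suicidal ideation or suicidal behaviour will be reported at baseline and during study treatment", and it names Visits 4, 6 and 10. On-treatment scores are compared with baseline and, at Visits 6 and 10, also with the last visit. The rule at issue follows: "An increase in C-SSRS total score to 4 or 5 will be considered as serious treatment-emergent suicidality". No formal test is planned.

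Section 9.3.4 lists the endpoints analysed by visit as "IPSS, Qmax, prostate volume, PSA, post void residual volume, suicidality and health outcomes". It requires both an LOCF and an At Visit analysis of these and makes LOCF primary. Section 7.4.6 specifies the since-last-visit version of the C-SSRS at Visits 4, 6 and 10.

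**The concern.** The protocol sets a numerical threshold on a score that it never constructs. A programmer has to choose a construction, and the choice decides who is called serious. Under none of the plausible constructions is a positive behaviour item serious in its own right. The serious row of a safety table could therefore read zero in an arm where the behaviour row beside it shows an attempt. The protocol itself expects few cases, so moving one case can change how that row reads.

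The LOCF listing raises a separate problem. A since-last-visit answer describes one interval. Carried forward, it becomes a statement about a later interval in which the man was not assessed.

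**Working it through.** There is no stated figure to reproduce. The check applies the rule to every possible answer pattern.

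**Inputs** (Suicidality text, section 9.3.7.2.1): ten binary items, 1-5 ideation and 6-10 behaviour; threshold 4 or 5. Only the level is tested. Requiring an increase as well can only narrow the label.

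**Pattern space.** There are 2^10 = 1024 patterns. Those with no behaviour item number 2^5 = 32, so 1024 - 32 = 992 include behaviour.

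**Reading A, highest category endorsed (1 to 10).** The highest is 4 in 2^3 = 8 patterns and 5 in 2^4 = 16 patterns, 24 in all. Any behaviour item makes the highest category at least 6, so none of the 24 includes behaviour.

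**Reading B, number of yes answers (0 to 10).**
- Total 4 or 5: C(10,4) + C(10,5) = 210 + 252 = 462 patterns. Ideation-only patterns among them: C(5,4) + C(5,5) = 6. So 456 of the 462 include behaviour.
- Behaviour patterns totalling 1 to 3: (10 + 45 + 120) - (5 + 10 + 10) = 150, not labelled.
- Behaviour patterns totalling 6 to 10: 210 + 120 + 45 + 10 + 1 = 386, not labelled if the threshold is read literally.
- Check: 150 + 456 + 386 = 992.

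With one behaviour item and k ideation items the total is k + 1:

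| k | Total | Labelled serious? |
|---|---|---|
| 0 | 1 | no |
| 1 | 2 | no |
| 2 | 3 | no |
| 3 | 4 | yes |
| 4 | 5 | yes |
| 5 | 6 | no, if literal |

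Read literally, one more positive answer can remove the label. If the threshold is taken to mean 4 or more, the 386 are recovered and the 150 are still missed, including the lone behaviour item.

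**Reading C, highest ideation category (1 to 5).** 24 × 32 = 768 patterns are labelled, of which 24 × 31 = 744 include behaviour, but only because of their ideation answers. The other 992 - 744 = 248 behaviour patterns are not labelled.

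These are counts of possible patterns, not probabilities.

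**LOCF.** Take a man whose last C-SSRS is at Visit 4. Under LOCF his answer is entered again at Visits 6 and 10. The by-visit counts then include two intervals without an assessment, and a comparison of a carried value with the last visit shows no change by construction. The outcomes defined over the whole treatment period are unaffected: a repeated yes adds no new subject, and a repeated no adds none.

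**The case against.** The strongest reply is that little can be lost. The same subsection counts behaviour separately, with any positive item sufficient. Section 7.4.6 sends possibly suicidality-related adverse events to a dedicated form. The serious adverse event definition in section 7.4.2 does not use the C-SSRS, section 7.4.1 has intentional overdose with possible suicidal intent reported whatever its sequelae, and the investigator reviews scores in real time. All of this stands. A reader might infer that an attempt could disappear from the safety report, or that this label is the only place to see it. The documents do not support that.

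A reader might also infer that the rule excludes behaviour on every reading. It does not: on the count of yes answers, which is the literal sense of a total over binary items, 456 of the 462 labelled patterns include behaviour. The ideation reading also fits a threshold of 4 or 5 on a five-step range, and the label would then simply grade ideation. But the protocol calls it suicidality and does not state that restriction.

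Section 9.3.7.2 leaves full safety detail to the analysis plan, which is not shown. That would answer a missing scoring rule. It does not answer a threshold that the protocol itself fixes on an undefined score.

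On LOCF, the At Visit analysis is also required. Section 9.3.7 says that later sections assign the approach, and the Suicidality text, unlike those for PSA and post-void residual volume, assigns none. This softens the point, but section 9.3.4 still names suicidality under an LOCF-primary rule.

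**Conclusion.** The point holds in limited form. The score is undefined; on two readings behaviour can never trigger the label, and on the third it does so only when the count happens to be 4 or 5. On all three, a lone positive behaviour item is not labelled serious. This rests only on the item structure that the protocol gives.

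The effect is confined to one descriptive safety label. It does not touch the primary endpoint, power, type I error, individual follow-up or serious adverse event reporting. The LOCF part affects by-visit counts and last-visit comparisons only; the stronger inference that carry-forward creates events in the any-time outcomes is not supported. Severity is minor to moderate.

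**What to change.** 1. In the Suicidality text of section 9.3.7.2.1, delete the reference to a total score. Define the 4-or-5 rule on the highest ideation category (1-5). Keep every increase to 4 or 5, including from 4 to 5, and keep the comparisons with both baseline and last visit.
2. State how Categories 6-10 enter. Either count positive behaviour items in the serious category, or rename the label serious treatment-emergent suicidal ideation and tabulate treatment-emergent behaviour beside it. The protocol does not list the five behaviour items, so the sponsor's safety physicians should choose between these.
3. In section 9.3.4, remove suicidality from the endpoints subject to LOCF. Report observed C-SSRS assessments only, including the End of Study Treatment assessment in section 7.2.2.5.

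The cost is a few lines of wording and matching table shells. No new data or visits are needed. The by-visit counts will have smaller denominators, which should be shown.

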#### 9.3.7.3. Health Outcomes Analyses

BPH-related quality of life (QOL) will be assessed using BPH-related Health Status, question 8 of IPSS (BHS), BPH Impact Index (BII) and sexual function with the Problem Assessment Scale of the Sexual Function Inventory (PAS SFI).

#### **BPH-related Health Status**

The BPH-related Health Status (BHS) score is collected on the IPSS questionnaire (Q8 of IPSS) and ranges from 0 to 6. Total BHS, change from baseline BHS, and percentage change from baseline BHS will be summarized by treatment group using both the LOCF and At Visit approaches at each scheduled post-baseline assessment. Change in baseline BHS will be compared at each scheduled post-baseline assessment using a general linear model with effects for treatment, cluster, and baseline BHS.

#### **BPH Impact Index**

The BPH Impact Index (BII) is the sum of four questions with a total score range of 0 to 13. Individual questionnaire missing responses will be imputed, if applicable, as defined in Section 9.3.7. Total BII, change from baseline BII, and percentage change from baseline BII will be summarized by treatment group using both the LOCF and At Visit approaches at each scheduled post-baseline assessment. Change in baseline BII will be compared at each scheduled post-baseline assessment using a general linear model with effects for treatment, cluster, and baseline BII.

#### **Problem Assessment Scale of the Sexual Function Inventory**

The Problem Assessment Scale of the Sexual Function Inventory (PAS SFI) is the sum of three questions each ranging from 0 to 4. Total score, change from baseline score, and percentage change from baseline will be summarized by treatment group using both the LOCF and At Visit approaches. Change in baseline score will be compared at each scheduled post-baseline assessment using a general linear model with effects for treatment, cluster, and baseline score.

#### 9.3.8. Medical Resource Utilisation

Summary statistics will be tabulated for the following:

- Incidence of hospital admissions for AUR and/or BPH-related surgical interventions; number and type of procedures carried out
- Length of hospital stay (in days, hours) associated with incidence of AUR and/or BPH-related surgical interventions and associated ward type

#### 9.3.9. Pharmacogenetic Analyses

Further details on PGx analyses will be addressed in Appendix 1 and the RAP.

## 9.3.10. Population Pharmacokinetic Analyses

Details on PPK analyses will be addressed in Appendix 7 and the RAP.

## 10. STUDY CONDUCT CONSIDERATIONS

# 10.1. Posting of Information on Publicly Available Clinical Trial Registers

Study information from this protocol will be posted on publicly available clinical trial registers before enrolment of subjects begins.

# 10.2. Regulatory and Ethical Considerations, Including the Informed Consent Process

Prior to initiation of a study site, GSK will obtain approval from the appropriate regulatory agency to conduct the study in accordance with applicable country-specific regulatory requirements.

The study will be conducted in accordance with Good Clinical Practice (GCP), all applicable subject privacy requirements, and the ethical principles that are outlined in the Declaration of Helsinki 2008, including, but not limited to:

- Institutional Review Board (IRB)/Independent Ethics Committee (IEC) review and approval of study protocol and any subsequent amendments.
- Subject informed consent.
- Investigator reporting requirements.

GSK will provide full details of the above procedures, either verbally, in writing, or both.

Written informed consent must be obtained from each subject prior to participation in the study. The contents and process of obtaining consent will be in accordance with all applicable regulatory requirements.

## 10.3. Quality Control (Study Monitoring)

In accordance with applicable regulations, GCP, and GSK procedures, the site will be contacted prior to the start of the study to review with the site staff the protocol, study requirements, and their responsibilities to satisfy regulatory, ethical, and GSK requirements. When reviewing data collection procedures, the discussion will include identification, agreement and documentation of data items for which the eCRF will serve as the source document.

The investigator and the head of the medical institution (where applicable) agrees to allow the monitor direct access to all relevant documents and to allocate their time and the time to their staff to monitor to discuss findings and any issues.

Monitoring visits will be conducted in a manner to ensure that the:

- Data are authentic, accurate, and complete.
- Safety and rights of subjects are being protected.
- Study is conducted in accordance with the currently approved protocol and any other study agreements, ICH GCP, and all applicable regulatory requirements.

## 10.4. Quality Assurance

RM2010/00134/05

To ensure compliance with ICH GCP and all applicable regulatory requirements, GSK may conduct quality assurance audits of the site. Regulatory agencies may conduct a regulatory inspection at any time during or after completion of the study. In the event of an audit or inspection, the investigator (and institution) must agree to grant the auditor(s) and inspector(s) direct access to all relevant documents and to allocate their time and the time of their staff to discuss any findings/relevant issues.

## 10.5. Study and Site Closure

The end of study is defined as last subject, last visit.

Upon completion or termination of the study, the monitor will conduct site closure activities with the investigator or site staff (as appropriate), in accordance with applicable regulations, ICH GCP, and GSK Standard Operating Procedures.

GSK reserves the right to temporarily suspend or terminate the study at any time for reasons including (but not limited to) safety issues, ethical issues, or severe noncompliance. If GSK determines that such action is required, GSK will discuss the reasons for taking such action with the investigator or head of the medical institution (where applicable). When feasible, GSK will provide advance notice to the investigator or head of the medical institution of the impending action.

If a study is suspended or terminated for **safety reasons**, GSK will promptly inform all investigators, heads of the medical institutions (where applicable),and/or institutions conducting the study. GSK will also promptly inform the relevant regulatory authorities of the suspension/termination along with the reasons for such action. Where required by applicable regulations, the investigator or head of the medical institution must inform the IRB/IEC promptly and provide the reason(s) for the suspension/termination.

#### 10.6. Records Retention

Following closure of the study, the investigator or head of the medical institution (where applicable) must maintain all site study records (except for those required by local regulations to be maintained elsewhere) in a safe and secure location. The records must be easily accessible when needed (e.g., for a GSK audit or regulatory inspection) and must be available for review in conjunction with assessment of the facility, supporting systems, and relevant site staff.

Where permitted by local laws/regulations or institutional policy, some or all of the records may be maintained in a format other than hard copy (e.g., microfiche, scanned, electronic); however, caution must be exercised before such action is taken. The

investigator must ensure that all reproductions are legible and are a true and accurate copy of the original. In addition, they must meet accessibility and retrieval standards, including regeneration of a hard copy, if required. The investigator must also ensure that an acceptable back-up of the reproductions exists and that there is an acceptable quality control procedure in place for creating the reproductions.

GSK will inform the investigator of the time period for retaining the site records in order to comply with all applicable regulatory requirements. The minimum retention time will meet the strictest standard applicable to a particular site, as dictated by local laws/regulations, GSK standard operating procedures, and/or institutional requirements.

The investigator must notify GSK of any changes in the archival arrangements, including, but not limited to archival of records at an off-site facility or transfer of ownership of the records in the event that the investigator is no longer associated with the site.

# 10.7. Provision of Study Results to Investigators, Posting to the Clinical Trials Register and Publication

Where required by applicable regulatory requirements, an investigator signatory will be identified for the approval of the clinical study report. The investigator will be provided reasonable access to statistical tables, figures, and relevant reports and will have the opportunity to review the complete study results at a GSK site or other mutually-agreeable location.

GSK will also provide the investigator with the full summary of the study results. The investigator is encouraged to share the summary results with the study subjects, as appropriate.

GSK will provide the investigator with the randomization codes for their site only after completion of the full statistical analysis.

The results summary will be posted to the Clinical Study Register no later than 12 months after the last subject's last visit (LSLV) or sooner if required by legal agreement, local law or regulation. In addition, a manuscript will be submitted to a peer-reviewed journal for publication within 18 months of LSLV. When manuscript publication in a peer-reviewed journal is not feasible, further study information will be posted to the GSK Clinical Study Register to supplement the results summary.

#### 12. APPENDICES

#### 12.1. Appendix 1: PGx

#### Pharmacogenetic Research

#### Pharmacogenetics - Background

Pharmacogenetics (PGx) is the study of variability in drug response due to hereditary factors in different populations. There is increasing evidence that an individual's genetic composition (i.e., genotype) may impact the pharmacokinetics (absorption, distribution, metabolism, elimination), pharmacodynamics (relationship between concentrations and pharmacologic effects or the time course of pharmacologic effects) and/or clinical outcome (in terms of efficacy and/or safety and tolerability). Some reported examples of PGx analysis include:

Drug	Disease	Gene	Outcome
Abacavir	HIV [Hetherington, 2002; Mallal, 2002]	HLA-B*5701	Individuals with HLA-B*5701 variant may be at increased risk for experiencing hypersensitivity to abacavir. Clinical assays are available for HLA-B*5701 but none has been validated. HLA-B*5701 screening would supplement but never replace abacavir clinical risk management strategies aimed at minimising rare but serious outcomes associated with abacavir hypersensitivity.
Warfarin	Cardiovascular [Neergard, 2006; Wilke, 2005]	CYP2C9	Serious Adverse Events (SAEs) experienced by some patients on warfarin may be explained by variations in the CYP2C9 gene that influences the degree of anticoagulation achieved.
Irinotecan	Cancer [FDA News Release, 2005]	UGT1A1	Variations in the UGT1A1 gene can influence a patient's ability to break down irinotecan, which can lead to increased blood levels of the drug and a higher risk of side effects. A dose of irinotecan that is safe for one patient with a particular UGT1A1 gene variation, might be too high for another patient without this variation, raising the risk of certain side-effects. A genetic blood test (Invader UGT1A1 molecular assay) is available that can detect variations in the gene.

A key component to successful PGx research is the collection of samples during the conduct of clinical studies.

"Collection of whole blood samples, even when no *a priori* hypothesis has been identified, may enable PGx analysis to be conducted if at any time it appears that there is a potential unexpected or unexplained variation in handling or response to the combination treatment of dutasteride and tamsulosin or tamsulosin monotherapy.

CONFIDENTIAL

